To guide the choice of surgical technique outcomes of mortality, adverse events and self-reported quality of life are important to report. As before mentioned LARS has significant impact on quality of life and is thus important to study. In order to evaluate the underlying mechanisms of LARS, and in the future provide effective treatments, it is central to evaluate the anorectal muscle function. Anorectal muscle function has been evaluated with anorectal manometry in patients who have been treated with low anterior resection at a median of 6 weeks (range 4-40 weeks) [12] and at a mean of 23 months (range 6-106 months) [13, 14] after surgery

Sexual dysfunction, urinary incontinence and fecal incontinence are present in patients with rectal cancer as long after surgery as 4 years, therefore it is important to determine if when these symptoms develop and how they are related to each other in patients treated for rectal cancer. [18] To our knowledge, no records exist on these relationships from prior to surgery to 2 years after low anterior resection. This type of information is central to the future design and conduct of expensive randomized trials.

Purpose

The primary purpose of the EDFI-Cohort study is to determine how several baseline variables (surgical technique, anorectal muscle function, faecal incontinence, urinary incontinence, sexual dysfunction, fatigue, physical activity, meaning in life and physical functioning) develop over time and predicts quality of life, and secondary how it predicts LARS-score in patients with rectal cancer from prior to surgery to 2 years after primary treatment.

Hypothesis

A priori, we determined the following major hypotheses for this study to be (with corresponding null hypotheses):

1. We expect to see poorer quality of life in patients with a higher LARS-score
2. Overall we expect to see poorer quality of life in patients with poor anorectal muscle function, faecal incontinence, urinary incontinence, sexual dysfunction, fatigue, low physical activity, low meaning in life and physical functioning.
3. We expect to a difference in quality of life and LARS-scores between surgical technique. We expect that PME will lead to fewer symptoms and TA-TME to worse symptoms compared with other techniques.
4. We expect to see no differences in mortality rate and adverse events between the different baseline variables.

Method

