Self-reported outcomes:

Information on education level, work status and civil status will be obtained through self-reported questionnaires at 3 weeks. The remaining self-reported outcomes is collected with a series of validated questionnaires that subjects will be asked to complete 6 times during the two year study, see table 1.

Quality of life of cancer patients (primary outcome) is assessed with questionnaires developed by the European Organisation for Research and Treatment of Cancer (EORTC). EORTC has developed and validated a generic core set (EORTC QLQ-C30) for assessing quality of life. [23] [24] As recommended by the EORTC, have added symptom specific module (EORTC QLQ-CR29) [23] and fatigue module (EORTC QLQ-FA12). [25] [26]

Bowel related quality of life (secondary outcome) is quantified with the Low Anterior Resection Symptom score (LARS-score), which is a validated score to group subjects into either no/low LARS or major LARS. [9] The items included in the LARS-score have been selected and weighted to reflect bowel related quality of life. [9] [27]

Faecal incontinence is also quantified with the St. Marks Incontinence score (also known as the Vaizey score), which is a validated instrument for assessing severity of faecal incontinence. [28]

Urinary incontinence is assessed with questionnaires developed by the workgroup International Consultation on Incontinence Modular Questionnaire (ICIQ). ICIQ has developed and validated a generic core set (ICIQ-UI) for assessing urinary incontinence. [29] Additionally, we use symptom specific modules also developed and validated by ICIQ. The modules assess urinary symptoms in males and females and sexual matters in males and females.

Physical activity level is quantified as done in the Danish National Health Profile – Health of the Danish People, which is a nationwide questionnaire answered by more than 180.000 Danish people in 2017. [30, 31]

Sources of meaning and meaningfulness is assessed with Sources of Meaning and Meaning in Life Questionnaire (SoMe), which is a self-reported measure of meaningfulness and crisis of meaning reported on two separate scales, enabling further analysis and comparisons of positive and negative aspects of meaning in life. The questionnaire has been validated in a Danish population. [32] [33]

Objective measures

All objective measures are to be collected at Slagelse Hospital and Zealand University Hospital, Køge, at 6 weeks, 6 months, 12 months and 24 months.

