Self-reported outcomes:	Questionnaire	Time point
Education level, work status and civil status	Non standardized questionnaire	3 weeks
Bowel related quality of life	Low anterior resection symptom – score (LARS-score)	3, 6, 12, 26, 52 and 104 weeks
Faecal incontinence	St. Marks Incontinence score (Vaizey-score)	3, 6, 12, 26, 52 and 104 weeks
Quality of life of cancer patients:	EORTC QLC-C30	3, 6, 12, 26, 52 and 104 weeks
Colorectal	EORTC QLQ-CR29	3, 6, 12, 26, 52 and 104 weeks
Fatigue	EORTC QLQ-FA12	3, 6, 12, 26, 52 and 104 weeks
Information about disease and treatment	EORTC QLQ-INFO25	3, 6, 12, 26, 52 and 104 weeks
Urinary Incontinence	International Consultation on Incontinence Modular Questionnaire (ICIQ) - Urinary Incontinence Short Form (ICIQ-UI SF)	3, 6, 12, 26, 52 and 104 weeks
Urinary symptoms, males	ICIQ-Male Lower Urinary Tract Symptoms (ICIQ-UI MLUTS)	3, 6, 12, 26, 52 and 104 weeks
Urinary symptoms, females	ICIQ-Female Lower Urinary Tract Symptoms (ICIQ-UI FLUTS)	3, 6, 12, 26, 52 and 104 weeks
Sexual dysfunction		

	Sexual dysfunction, males	ICIQ-Male Sexual Matters associated with Lower Urinary Tract Symptoms (ICIQ-UI MLUTSsex)	3, 6, 12, 26, 52 and 104 weeks
	Sexual dysfunction, females	ICIQ-Female Sexual Matters associated with Lower Urinary Tract Symptoms (ICIQ-UI FLUTSsex)	3, 6, 12, 26, 52 and 104 weeks
	Physical activity level	physical activity section of the Danish National Health Profile	3, 6, 12, 26, 52 and 104 weeks
	Sources of meaning and meaningfulness	Sources of Meaning and Meaning in Life Questionnaire (SoMe)	3, 6, 12, 26, 52 and 104 weeks

Objective measure:	Units:	Time point
Anorectal muscle function (digital examination)		
Maximal resting pressure Maximal squeeze pressure Endurance squeeze - max squeeze pressure or longest time Latency (rate of force development), number of rectal muscle contractions/squeezes in 15 sec test.	0-5 (DRESS) (lowest to highest) 0-5 (DRESS) (lowest to highest) 0-5 (DRESS) and s, maximum of 60 s. n	6, 26, 52 and 104 weeks
Anorectal muscle function (High-Resolution AnoRectal Manometry)		
Pressure measurements: Maximal resting pressure Maximal squeeze pressure Maximal squeeze pressure duration	mmHg mmHg s	6, 26, 52 and 104 weeks
Volume capacity measurements: Maximal tolerated volume Conscious rectal sensitivity threshold Conscious rectal sensitivity Constant sensation	mL mL % of maximal volume mL	6, 26, 52 and 104 weeks
Physical Performance		
6-Minute Walk test	M	6, 26, 52 and 104 weeks

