Statistical analysis

We plan to analyze the EDFI-Cohort study as repeated measures with both simple and multiple linear regression models for the continuous data. We plan to adjust for the following known confounders: patient characteristics: age at surgery, gender, tumor height, tumor stages and variables related to treatment: surgical complications (e.g. nerve damage, sphincter rupture), additional radiotherapy/chemotherapy, time with stoma.

Patient involvement

Prior to planning of the EDFI-Cohort study, we have performed a single case-study (spring 2016) on examination procedure, questionnaires and pelvic floor muscle rehabilitation. This case provided us with valuable information on testing and possible evaluation of treatment effect. In the winter of 2017-18, we

interviewed subjects on their perspective on this study design and examination load. In the same time-period, we did pilot testing on the clinical examinations.

Research ethics

Examinations included in this study are all associated with very few, if any, adverse events, except from the mild discomfort related to the clinical anorectal examination itself. Subjects included in this study will receive four examinations, whereas care as usual at Slagelse and Køge Hospital usually include one examination/contact to the local LARS clinic with no anorectal examination. This, included subjects are more closely monitored and, if need be, might receive relevant treatment earlier compared to care as usual patients.

Future implications

Results from the EDFI-Cohort study will help guide the design of randomized controlled trials on treatments of faecal incontinence in subjects who have been surgically treated for rectal cancer. With emphasis on establishing the role of anorectal muscle function in the development of faecal incontinence.

Applicability of registrations and approvals

A prior version of the EDFI-Cohort study protocol has been approved by the regional research ethics committee of Region Zealand and The Data Protection Agency journal number: REG-130-2017. This project adhere to the General Data Protection Regulation and Data Protection Act. The regional research ethics committee and data protection agency will need to approve the new version of the study protocol prior to project start. Finally, the project will, prior to start, be registered at ClinicalTrials.gov. This study is part of the patient compensation scheme (patienterstatningsordningen).

Study economy

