This study is partially funded. Funding has so far come from the local research fund of NSR hospitals (DKK 968,000) and The Association of Danish Physiotherapists (DKK 82,000). The Department of Physiotherapy and Occupational Therapy at Slagelse Hospital provides access to facilities and offices. None of the funding agencies have any influence on study design or reporting of data. Further funding will be applied for from public and private foundations.

To reduce unnecessary inconvenience for subjects, we have planned the study test sessions on same days as subjects are to meet in the LARS outpatient clinics.

Dissemination of study results:

The EDFI-Cohort study is expected to be presented at several conferences for health professionals and the public and to provide 4 international peer-reviewed scientific papers on the findings whether they are positive, negative or inconclusive. All reporting of the EDFI-Cohort study will comply with the STROBE-guidelines [40, 41].

The first publication (paper 1) will report on associations between quality of life and LARS-score, adjusted for baseline variables (surgical technique, anorectal muscle function, faecal incontinence, urinary incontinence, sexual dysfunction, fatigue, physical activity, meaning in life and physical functioning) from prior to curative surgery until 12 weeks after surgery.

The second publication (paper 2) will report on the development of quality of life and LARS-score, stratified based on choice of surgical technique prior to curative surgery until 6 months after surgery.

The third publication (paper 3) will report on associations between quality of life and LARS-score, adjusted for baseline variables (surgical technique, anorectal muscle function, faecal incontinence, urinary incontinence, sexual dysfunction, fatigue, physical activity, meaning in life and physical functioning) from prior to curative surgery until 2 years after surgery.

The fourth publication (paper 4) will report on mortality rate and adverse events adjusted for baseline variables (surgical technique, anorectal muscle function, faecal incontinence, urinary incontinence, sexual dysfunction, fatigue, physical activity, meaning in life and physical functioning) from prior to curative surgery until 2 years after surgery.

References

1. Annual report 2017, in *Danish Colorectal Cancer Group*, D.C.C. Group, Editor. 2017, The Danish Clinical Registries and Danish Multidisciplinary Cancer Groups.

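### Anorectal muscle function is treated as a baseline predictor but first examined at week 6, so the week-3 quality-of-life and LARS scores come before it

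*Protocol*

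**What the plan says.** **Outcome schedule.** The Self-reported outcomes section says of the questionnaires that "subjects will be asked to complete 6 times during the two year study, see table 1". Table 1 lists the QLQ-C30 (primary outcome), the LARS-score (secondary outcome) and the other repeated questionnaires at "3, 6, 12, 26, 52 and 104 weeks".

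**Examination schedule.** The Objective measures section states "All objective measures are to be collected at Slagelse Hospital and Zealand University Hospital, Køge, at 6 weeks, 6 months, 12 months and 24 months". Table 1 gives "6, 26, 52 and 104 weeks" for digital examination, manometry and the six-minute walk test (6MWT). Research ethics agrees: "Subjects included in this study will receive four examinations".

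**Role of muscle function.** The Purpose section lists it among baseline variables and asks how these "develop over time and predicts quality of life, and secondary how it predicts LARS-score". Hypothesis 2 names it, and both power statements under Sample size use high against low muscle function as a contrast. Under Dissemination of study results: "The first publication (paper 1) will report on associations between quality of life and LARS-score, adjusted for baseline variables (surgical technique, anorectal muscle function", with the list continuing to physical functioning. Paper 1 covers the period "from prior to curative surgery until 12 weeks after surgery". Paper 3 uses the same covariates up to two years.

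**Pre-surgery values.** The Patient records section and Table 1 take manometry, digital examination and 6MWT from hospital records if they are available. The Method section has patients invited around or after discharge, so no study examination precedes surgery.

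**The concern.** A baseline predictor should be measured at or before the first outcome that it is said to predict. Here the first scheduled examination falls three weeks after the first outcome questionnaire. A repeated-measures model that includes week 3 and uses the week-6 examination as baseline relates an earlier outcome to a later measurement. That association can be described, but it is not prediction, and it would be averaged with the correctly ordered visits in one coefficient.

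Muscle function is not an incidental covariate. It is named in the purpose, in a hypothesis and in the power statements, so how its coefficient may be read matters for the study's main message.

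**Working it through.** **Inputs**
- Questionnaire weeks (Table 1): 3, 6, 12, 26, 52, 104, which makes 6 rounds, as the text states.
- Examination weeks (Table 1): 6, 26, 52, 104, which makes 4 examinations, as the text and Research ethics state.
- Expected recruitment (Sample size): 70 patients.
- Window (Dissemination): paper 1 to week 12, paper 3 to week 104.
- Assumptions: both schedules count from the same origin, and every patient attends every visit. The second makes the counts upper limits.

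**Step 1, order of measurement.** Each outcome visit is compared with the first scheduled examination, at week 6.

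| Outcome visit | Relation to the week-6 examination |
|---|---|
| Week 3 | 6 − 3 = 3 weeks before it |
| Week 6 | concurrent |
| Week 12 | 12 − 6 = 6 weeks after it |
| Weeks 26, 52, 104 | after it |

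**Step 2, size in paper 1.** The outcome visits are weeks 3, 6 and 12.
- Total: 70 × 3 = 210 person-visits.
- Before the predictor (week 3): 70 × 1 = 70, and 70/210 = 33%.
- Concurrent with it or after it (weeks 6 and 12): 70 × 2 = 140, and 140/210 = 67%.

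**Step 3, size in paper 3.** All six visits count.
- Total: 70 × 6 = 420 person-visits.
- Before the predictor: 70, and 70/420 = 17%.

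**Step 4, effect of the record data.** The protocol gives no expected share of patients with a pre-surgery examination on record. Let this share be f, an assumption. The week-3 person-visits without any earlier value number 70 × (1 − f):
- f = 0: 70
- f = 0.5: 35
- f = 1: 0

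Even where a record value exists, it describes function before the operation, not function at week 3 after it.

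**Step 5, late entry.** For patients invited by letter, the second letter follows after two weeks and the phone call 2–3 weeks later, so 4–5 weeks after the first letter. Those who join only at the call cannot give a timely week-3 questionnaire. This also makes 70 an upper limit.

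**The case against.** The strongest case on the other side has five parts.

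- **A baseline covariate needs only one value.** This stands. One examination within paper 1's window is not a fault in itself, and the week-6 value properly precedes week 12. A reader might infer that only week 6 is usable, so 70 of 210 person-visits, and that most of paper 1's data would be lost. That holds only in a strictly concurrent model with a time-varying covariate, which the protocol does not specify.
- **Pre-surgery record values precede week 3.** This stands for patients who have them. They are optional, the Patient records section describes their use as characterising patients, and Research ethics says the usual LARS-clinic contact involves no anorectal examination. They cannot be relied on as a baseline for the cohort.
- **The alignment of visits and covariates belongs in the analysis plan.** This stands in part. An analysis plan can exclude week 3, but it cannot create an earlier measurement. The schedule, the word baseline and paper 1's window are all fixed in the protocol.
- **Paper 1 is about association, not prediction.** This stands for paper 1 as worded. Muscle function is one of nine adjustment variables there, and the predictive role comes from Purpose and hypothesis 2. Both main scores exist at all three visits, so that association needs no rescue.
- **This is only the missing pre-surgery baseline again.** The two are related: a guaranteed pre-surgery examination would restore the order. But if the first postoperative examination is accepted as baseline, week 3 still precedes it.

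Two wider readings also fail. Paper 2 is stratified by surgical technique and does not list muscle function as a covariate, so it is not affected. And the 6MWT is not clearly the physical functioning covariate: Table 1 files it under physical performance, while the QLQ-C30 has a physical function subscale collected at every round.

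**Conclusion.** The point holds for week 3 only. The protocol calls muscle function a baseline predictor but first schedules it three weeks after the first outcome. Up to 70 of 210 person-visits in paper 1 and up to 70 of 420 in paper 3 precede it. Weeks 6 and 12 in paper 1, 140 person-visits, are in order.

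The same holds for the 6MWT if, and only if, it is the measure behind physical functioning. Predictors taken from questionnaires are not affected, because they are collected at every round.

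The counts rest on 70 patients with full attendance and no usable pre-surgery records. Record data, missed visits or late entry make them smaller. The documents do not show how far the estimates would move, and no size of bias is claimed. A reader might also infer that the examination schedule has to change. It does not: having fewer examinations than questionnaires is a reasonable choice in a study that consulted patients about examination load.

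**What to change.** Change the wording in Purpose, Statistical analysis and Dissemination of study results:

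1. Define week 6 as the starting point of any model that includes anorectal muscle function or the 6MWT. Read week 6 as concurrent association, and weeks 12, 26, 52 and 104 as prediction from the week-6 value.
2. Do not use week-3 scores as an outcome in those models. They may enter as an earlier adjustment value.
3. Do not call the week-6 examination baseline, or a predictor, with respect to week 3.
4. Keep paper 1's association between quality of life and LARS-score at weeks 3, 6 and 12, using covariates available by week 3 (surgical technique and questionnaire scores). Add muscle function only in the model from week 6 onward. Recasting the whole paper as week-6 predictors of week-12 outcomes is not needed and would replace its stated question.
5. State which measure represents physical functioning in papers 1 and 3.

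The cost is text only, with no new visit, procedure or burden for patients. The small downside is that week-3 outcomes drop out of the muscle-function models: up to 70 of 210 person-visits in paper 1 and 70 of 420 in paper 3.

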Subjects for the EDFI-Cohort study will be recruited during 2019 and 2020 from Department of Surgery, Slagelse, and Zealand University Hospital, Køge. Subjects need to be diagnosed with rectal cancer and have received curative surgery (low anterior resection) with/without adjuvant (radiation/chemo) therapy. Subjects for this study are to meet the following inclusion criteria: Low anterior resection (e.g. not limited to total mesorectal excision (TME) or partial mesorectal excision (PME)), ability to communicate in Danish, adults (> 18 years of age), and American Society of Anaesthesiologists (ASA) score: I-IV. Exclusion criteria are: ASA score of: V-VI.

Prior to inclusion, subjects must provide written informed consent to participate in this study.

Subjects for the EDFI-Cohort study will be identified through surgical codes at Slagelse Hospital and Zealand University Hospital, Køge, Denmark. Eligible subjects will primarily be invited to participate in this study prior to discharge with oral and written information, provided in person by a health professional from the research group. Alternatively eligible subjects will be sent a letter after discharge. The letter and written information contain information on the study, the right to say no to the study, the right to 24 hours reflection time and the right to bring next of kin or another person of the subject's choice with him/her to the inclusion meeting. Potential subjects that are only invited by letter are asked to contact the research group for further information. A second letter will be sent to potential subjects whom have not contacted the research group within two weeks, and 2-3 weeks after the second letter has been sent, subjects will be contacted once by phone. Verbal and written information will be provided by a health professional from the research group at a meeting in an undisturbed examination room at Slagelse Hospital or Zealand University Hospital, Køge, Denmark.

Sample size:

The cohort will recruit all eligible patients from summer 2019 to April 2020. In this time period we estimate to recruit 70 patients to the EDFI cohort. A total of 86 patients were surgically treated for rectum cancer in 2017 at Slagelse Hospital and Zealand University Hospital, Køge.

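### The named confounder list leaves out hospital and ASA grade, so site confounding of the technique and muscle-function contrasts is possible, though not demonstrated, and goes unadjusted

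*Protocol*

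**What the plan says.** The Statistical analysis section introduces its list with "We plan to adjust for the following known confounders". The list starts "age at surgery, gender, tumor height, tumor stages and variables related to treatment: surgical complications" and closes with "additional radiotherapy/chemotherapy, time with stoma". The section on dissemination gives a second set of adjustment variables for papers 1, 3 and 4: "surgical technique, anorectal muscle function, faecal incontinence, urinary incontinence, sexual dysfunction, fatigue, physical activity, meaning in life and physical functioning". Hospital and ASA grade are in neither set, and the protocol mentions no stratification or random effect by hospital.

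Two hospitals supply the whole study. Under Method, subjects are "recruited during 2019 and 2020 from Department of Surgery, Slagelse, and Zealand University Hospital, Køge" and "identified through surgical codes at Slagelse Hospital and Zealand University Hospital, Køge, Denmark". Under Objective measures, "All objective measures are to be collected at Slagelse Hospital and Zealand University Hospital, Køge". Research ethics describes usual care at both hospitals in a single sentence, as "one examination/contact to the local LARS clinic with no anorectal examination".

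ASA grades I to IV are eligible (Method), and the grade is taken from patient records as descriptive information (Outcomes and Table 1). Hypothesis 3 makes technique a directional contrast: partial mesorectal excision is expected to do better and transanal TME worse.

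**The concern.** This is a cohort, so technique is not assigned at random. If one technique is used more at one hospital, and outcomes differ between the hospitals for any reason not on the list, a model without hospital credits part of that difference to the operation. The same holds for muscle function. The 0 to 5 digital score depends on the examiner, so if scoring differed by site, the high and low groups would partly encode hospital. The protocol wants its results to guide the choice of technique and the design of later randomised trials, so a misattributed difference would matter.

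ASA grade raises a different and smaller question. General fitness plausibly affects quality of life and also several of the predictors studied, such as activity, fatigue and walking distance. An association between them may then partly reflect comorbidity. Differences in hospital care play no part in that mechanism.

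**Working it through.** **Inputs from the protocol.** About 70 patients in total; two-sided 5% level; two-sample pooled t-test; SD 22 and target 10 points for the QLQ-C30 scale; SD 12 and target 6 points for LARS (Sample size section).

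**Inputs assumed.** The protocol gives no hospital effect and no split of technique by hospital. I assume that outcomes differ between the hospitals by g = 3 or 5 points for reasons outside the list. I let the imbalance d vary, where d is the share of patients from one hospital in one technique group minus that share in the other. I also assume 35 patients per technique group.

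**The protocol's own figures.** It gives no figure for site effects. Its power figures of 0.98 (quality of life) and 0.99 (LARS) do not reproduce with 35 per group:
- Quality of life: standard error 22 × √(2/35) = 5.26, noncentrality 10/5.26 = 1.90, power 0.47.
- LARS: standard error 12 × √(2/35) = 2.87, noncentrality 6/2.87 = 2.09, power 0.54.

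That discrepancy is a separate matter. I use 0.47 and 0.54 below as the baseline.

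**Bias without hospital in the model.** Spurious technique difference = g × d.

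| Imbalance d | g = 3 | g = 5 |
|---|---|---|
| 0 | 0 | 0 |
| 0.2 | 0.6 | 1.0 |
| 0.5 | 1.5 | 2.5 |
| 0.8 | 2.4 | 4.0 |

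At d = 0.5 and g = 5 the bias is 2.5/10 = 25% of the quality-of-life target and 2.5/6 = 42% of the LARS target. With 35 per group and SD 22, a spurious 2.5 points raises the 5% false-positive rate for quality of life to about 7.6%.

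**Cost of adding hospital.** With equal margins, the variance of the technique estimate is multiplied by 1/(1 − d²): 1.04 at d = 0.2, 1.33 at 0.5 and 2.78 at 0.8.

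| Imbalance d | Power, 10 quality-of-life points | Power, 6 LARS points |
|---|---|---|
| 0 | 0.47 | 0.54 |
| 0.2 | 0.45 | 0.52 |
| 0.5 | 0.37 | 0.43 |
| 0.8 | 0.20 | 0.24 |

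At d = 1, with each technique confined to one hospital, the variance factor is undefined. The two effects cannot be separated by any model.

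**The case against.** The strongest reply is that the mechanism is conjecture. The protocol describes usual care at both hospitals in the same words, refers to one research group, and applies one examination schedule. It does not say that examiners or the mix of techniques differ by site. That stands. A reader might infer from two operating hospitals and a local clinic that each runs its own care and that the technique results will be biased, but the text does not support this.

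Second, several routes by which a hospital could act are already covered: stoma time, surgical complications, radiotherapy/chemotherapy and tumour height are all on the list. That also stands, and it narrows what an unlisted hospital effect could contain.

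Third, the list is not declared exhaustive, the papers bring in further variables, and a centre term could be left to an analysis plan. This stands only in part. The protocol names a specific set of confounders and then a second set, and both omit two baseline variables already to hand.

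Fourth, adjustment costs most precision exactly where it would matter. That is true and must be stated. But the wider interval reflects real uncertainty about technique when it is tied to hospital, and is no reason to leave hospital out.

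Fifth, ASA grade overlaps with age, activity, fatigue and physical functioning, and the stated aim is partly predictive. This supports treating ASA as minor, not ignoring it.

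**Conclusion.** The point holds as an omission with a possible consequence. The named adjustment sets lack hospital and ASA grade in a non-randomised two-hospital cohort, and both can be added without new data collection.

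Site confounding of the technique and muscle-function contrasts is not demonstrated. Under assumed hospital differences of 3 to 5 points it runs from 0, if technique is balanced, to about 2.5 points at an imbalance of 0.5. Both the hospital difference and the imbalance are my assumptions.

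A reader might take the possible bias to be as large as the full hospital difference, up to 5 points. That requires complete separation of technique by hospital, which the protocol does not suggest and which a covariate could not repair. Nor should the ASA omission be read as part of the site problem: it is a separate and smaller matter of comorbidity.

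**What to change.** In the Statistical analysis section:

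- Add hospital as a fixed covariate to the multiple regression models, and show the estimate without hospital alongside.
- Report a table of technique by hospital. If a technique is confined to one hospital, state that its effect cannot be separated from that of the hospital.
- As a separate, minor change, add ASA grade as a covariate in the quality-of-life models.

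This changes wording only. Hospital is known from how patients are identified, and ASA grade is already recorded. The statistical cost is about two degrees of freedom: one for hospital and one for ASA if it enters as a single term. The interval for technique also widens when technique is strongly tied to hospital. With 35 per group, power for 10 quality-of-life points falls from about 0.47 to 0.37 at an imbalance of 0.5 and to 0.20 at 0.8. Showing both estimates lets the reader see that trade-off.
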